3.0 PATIENT SELECTION

3.1 Inclusion Criteria

- 3.1.1 Pathologic proven diagnosis of solid tumor malignancy.
- 3.1.2 Age ≥ 18 .
- 3.1.3 KPS ≥ 70 .
- 3.1.4 Mini Mental Status Exam (MMSE) ≥ 18 prior to study entry.
- 3.1.5 RPA class I (KPS ≥ 70 , primary cancer controlled, age < 65 , metastases in brain only) or class II (lack of one or more of class I criteria) (see **Appendix A** for definitions).
- 3.1.6 One to ten brain metastatic lesions.

3.2 Exclusion Criteria

- 3.2.1 Previous whole brain radiation therapy
- 3.2.2 Previous radiosurgery to any currently progressive gross metastatic disease
- 3.2.3 Previous radiosurgery to any intracranial site within the prior 6 weeks
- 3.2.4 RPA class III (KPS < 70 , see **Appendix A**).
- 3.2.5 Radiosensitive (eg. small cell lung carcinomas, germ cell tumors, leukemias, or lymphomas) or unknown tumor histologies.
- 3.2.6 Concurrent chemotherapy (no chemotherapy starting 14 days before start of radiation)
- 3.2.7 Evidence of leptomeningeal disease by MRI and/or CSF cytology.
- 3.2.8 Current pregnancy
- 3.2.9 No metastases to brain stem, midbrain, pons, or medulla or within 7 mm of the optic apparatus (*optic nerves and chiasm*).

4.0 PRE-TREATMENT EVALUATION

- 4.1 MRI scan with and without contrast (at least 5mm resolution on T1 post-contrast imaging).
- 4.2 History and physical including a detailed neurologic exam.
- 4.3 Steroid and anti-convulsant doses must be documented.
- 4.4 Baseline MMSE.
- 4.5 Baseline neurocognitive function using the HVLT-R (memory).
- 4.6 Baseline neurocognitive function using MOS (self-report).
- 4.7 Baseline QOL assessment using FACT-Br.
- 4.8 Documentation of extent of systemic disease.
- 4.9 Pregnancy test in women of child bearing potential when there is clinical suspicion of pregnancy

5.0 REGISTRATION

This will be a single cohort pilot study. Safety of the chosen dose level has been shown based on the previous phase I dose escalation iteration of this study.

18 patients will be enrolled consecutively into this single arm pilot study.

6.0 RADIATION THERAPY

6.1 Localization, Simulation, and Immobilization

6.1.1 Patient immobilization

The patient shall be treated in the supine or other appropriate position for the location of the lesion. A standard head-holding device involving a thermoplastic mask that is transparent to x-rays will be used to ensure adequate immobilization during therapy and daily reproducibility.

6.1.2 Simulation CT scan

At simulation, a non-contrasted CT scan with at least 1.25mm resolution will be obtained.

6.1.3 MRI scan

A post-contrast T1 MRI series with at least 5 mm resolution will be required for study entry. This image series will be fused/registered with the simulation CT scan using appropriate software.

6.1.4 Target definition

Target/tumor volumes will be contoured. Target volumes shall include the whole brain parenchyma inferiorly bordered by the foramen magnum with boost to gross metastatic tumor(s) as defined by the post-contrast T1 weighted MRI. The whole brain CTV will be expanded by 3 mm to create the whole brain PTV. Each metastatic tumor GTV will be expanded by 2 mm to obtain the planning target volumes (PTVs) for the boost targets.

6.1.5 Daily patient setup

Patients will be setup with daily on-board imaging guidance. This will involve obtaining orthogonal kV images prior to each treatment fraction and making appropriate adjustments to ensure treatment setup accuracy.

6.2 Technical Factors

6.2.1 X-ray energy

Treatment shall be delivered with megavoltage machines of energy ranging from 6MV up to and including 18 MV photons. Selection of the appropriate photon energy should be based on optimizing the RT dose distribution within the target volume and minimizing dose to non-target normal tissues.

6.2.2 Hardware configuration

Treatment will be delivered via volumetric modulated arc therapy (Rapid Arc) with 1-3 arcs with rotations up to 358°. Collimator will be turned at 45° for the planning.

6.3 Dose specifications

6.3.1 Planning goals

Goal is to obtain 95% PTV coverage with the prescription dose with a D_{min} to PTVs of 90% of the prescribed dose. Whole brain PTV will be prescribed 25 Gy. The boost PTV(s) will be prescribed according to the dose escalation scheme described below. In the optimization process, dose to the brain outside of the boost PTV should be minimized as much as possible while maintaining the dose prescription goals listed above.

6.3.2 Dose

This cohort is based on giving 25 Gy in 10 fractions to the whole brain** (see below). The efficacy and tolerability of this fractionation has also been established.

Group	Dose (to lesions)	SIB dose/fx	BED ₁₀	BED ₃	Patients
Brain dose	2.5 Gy x 10 fx		31.25	45.83	
** resection cavity	3 Gy x 10 fx	0.5 Gy SIB			
Cohort group	4.5 Gy x 10 fx	2 Gy SIB	65.25	112.5	18

Gy, Gray; fx, fraction; SIB, simultaneous in-field boost; BED₁₀, biologically equivalent dose for α/β of 10 (response of tumor, or early-reacting tissue); BED₃, biologically equivalent dose for α/β of 3 (response of late-reacting tissue).

** If a patient has had brain metastases resected that is part of the whole brain volume, then that resection cavity with a 2mm PTV expansion will be boosted to a total of 30 Gy in 10 fx with a 0.5 Gy SIB / fx over the whole brain 25 Gy in 10 fx baseline.

6.4 **Critical Structures**

Dose specification to be used in the treatment planning process to limit dose to critical structures are as follows: 1) the lens (<10 Gy), 2) globes (<30 Gy), 3) optic chiasm/nerves (<37 Gy), 4) brainstem (90% < 37 Gy), and 5) cervical spinal cord (<36 Gy)

6.5 **Radiation Adverse Events**

6.5.1 Acute (≤ 90 days from treatment start)

Expected adverse events include sore throat, hair loss, erythema of the scalp, headache, nausea and vomiting, lethargy, and transient worsening of neurological deficits. Reactions in the ear canals and on the ear should be observed and treated symptomatically.

6.5.2 Late (> 90 days from treatment start)

Possible adverse events include radiation necrosis, cognitive dysfunction, visual difficulties, accelerated atherosclerosis, and radiation-induced neoplasms.

7.0 DRUG THERAPY

Corticosteroid and anti-convulsant use will be documented.

8.0 SURGERY

Not applicable to this protocol.

9.0 OTHER THERAPIES

Not applicable to this protocol.

10.0 PATHOLOGY

All patients will have a pathologically documented malignancy prior to initiating therapy.

11.0 PATIENT ASSESSMENTS

11.1 Neurocognitive Assessments

11.1.1 Tests to be administered

Cognitive Domain	Assessment
Memory	Hopkins Verbal Learning Test-Revised
Global Function	Mini-Mental Status Examination
Cognitive Function (self-report)	Medical Outcomes Cognitive Scale

11.1.2 Hopkins Verbal Learning Test- Revised (HVLT-R)

The patient learns 12 words read to them 3 times; free recall is tested after each learning trial. Delayed recall is evaluated after 20 minutes. Following the delayed recall trial, the patient completes a delayed recognition test to determine if an impairment of delayed recall is due to a retrieval deficit or to a consolidation deficit. Entire test requires about 5 minutes to complete.

11.1.3 Mini-Mental Status Examination (MMSE)

This is a brief, standardized tool to grade patients' global cognitive function. The MMSE begins with an assessment of orientation to place and time. Next is a test of memory (immediate recall) by having the subject immediately repeat the names of 3 objects presented orally. Following this, the patient subtracts sevens serially from 100. The subject is then asked to recall the three items previously repeated (delayed recall). The final section evaluates aphasia and apraxia by testing naming, repetition, compliance with a 3-step command, comprehension of written words, writing, and copying a drawing. The maximum score that can be obtained for the entire MMSE is 30 points.

11.1.4 Cognitive Functioning Subscale of the Medical Outcomes Scale (MOS)(Self-report)

This 6-item, self-report measure is designed to measure day-to-day cognitive functioning of which the patient would be aware, including difficulty with problem-solving, slowed reaction times, forgetfulness, and concentration. Reliability and validity have been reported for patients with cancer. Scale is based on multiple choice questions asking about cognitive function where the item is present 1= all of the time to 6=none of the time. Scored in five steps (data cleaning, changing out of range values to missing, item re-calibration and skip pattern recording, reverse scoring of items so that the highest score reflects the best health state, transforming

scores linearly to a common metric with a range of 0-100, averaging across items in the same scale). Completion time is estimated to be less than 5 minutes.

11.1.5 Frequency of neurocognitive assessments

All tests will be given at baseline and at every follow-up for the first 6 months, then every 6 months thereafter (at 1, 3, 6, 12, 18, and 24 months). A window period of +/- 6 weeks will be allowed to correlate with each study time-point visit.

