11.2.2 Frequency of QOL assessment

The FACT-Br will be given at baseline and at every follow-up for the first 6 months, then every 6 months thereafter (at 1, 3, 6, 12, 18, and 24 months). A window period of +/- 6 weeks will be allowed to correlate with each study time-point visit.

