11.3 Toxicity and Outcome Assessments

11.3.1 Imaging followup

Patients will undergo brain MRI prior to study entry and at 1 month, 3 months and every 3 months thereafter or when otherwise indicated (eg. at onset of clinical deterioration). A window period of +/- 6 weeks will be allowed to correlate with each study time-point MRI.

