13.1.2 Secondary Endpoints (to be compared with standard historical controls)

- Progression-free survival
- Overall Survival
- Neurocognitive effects
- QOL outcomes

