13.2 Sample size

This will be a single cohort pilot study. Safety of the chosen dose level has been shown based on the previous phase I dose escalation iteration of this study.

18 patients will be enrolled consecutively into this single arm pilot study.

If a patient is not able to complete follow up to the toxicity assessment point of 4 months due to a toxicity judged not to be at least possibly related to therapy, then that patient will be replaced by the next patient enrolled.

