13.3 Statistical Analysis

Descriptive statistics will be performed on the clinical and treatment factors on subjects on this study. Categorical data will be presented on frequency tables while continuous data will be presented as mean, standard deviation, median and range. Local control, regional brain control, progression-free survival and overall survival will be assessed using the Kaplan-Meier method with censoring as appropriate. Univariate and multivariate analysis will be performed with these endpoints to determine patient factors that may influence outcome. These curves will also be compared to previously published results as historical controls. The results of the neurocognitive and quality of life surveys/tests will be plotted for each patient to assess for a general trend over time. The trend over time can also be analyzed by linear regression analysis. Each point in time can be compared with historical controls using a student's t-test to determine whether there is a significant difference in the survey/test scores in patients on our study versus historical results.

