APPENDIX C - Timeline

Note:). A window period of +/- 6 weeks will be allowed to correlate with each study time-point and MRI visit.

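### Does the flat ±6-week window leave early cognitive and quality-of-life scores without a clear visit label?

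*Combined protocol and SAP*

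**What the plan says.** Section 11.1.5 schedules HVLT-R, MMSE and the MOS cognitive scale at baseline, at the follow-ups in the first half-year, and "then every 6 months thereafter (at 1, 3, 6, 12, 18, and 24 months". It then adds: "A window period of +/- 6 weeks will be allowed to correlate with each study time-point visit". Section 11.2.2 ties the questionnaire to the same visits ("The FACT-Br will be given at baseline and at every follow-up for the first 6 months") and repeats the window. Section 11.3.1 gives imaging the same tolerance ("A window period of +/- 6 weeks will be allowed to correlate with each study time-point MRI"), and so does the note in Appendix C: "A window period of +/- 6 weeks will be allowed to correlate with each study time-point and MRI visit".

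On analysis, Section 13.3 plots the cognitive and quality-of-life results for each patient, allows a regression over time, and adds that "Each point in time can be compared with historical controls" by t-test. These outcomes are listed in Section 13.1.2 under "Secondary Endpoints (to be compared with standard historical controls". Section 13.2 gives the scale of the study: "18 patients will be enrolled consecutively into this single arm pilot study".

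**The concern.** A visit window normally serves to give each assessment one place in the schedule. A half-width of 6 weeks is harmless between visits 3 or 6 months apart, but the first two visits are only 2 months apart. A test done in week 9 is within tolerance for both the 1-month and the 3-month visit, and the readable text does not say which should claim it, or which test counts if two fall in one window. Read literally, the 1-month window also opens before the follow-up clock starts.

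At stake would be the comparisons with historical controls at each time point, which need every score to belong to one visit. With 18 patients, moving one score shifts a group mean noticeably, and a label chosen after the score is known could favour one result. Missed early visits are foreseeable, since Section 12.2 takes patients off study for local CNS progression, death, their own request or discharge to hospice.

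**Working it through.** **Inputs.** Half-width: 6 weeks = 42 days (Sections 11.1.5 and 11.2.2). Targets: 1, 3, 6, 12, 18 and 24 months (same sections). The documents do not define a month in days. I take m = 365.25/12 = 30.4375 days and show the range 28 to 31. The plan states no figure for the overlap, so there is none to reproduce.

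**Windows.** The window for month k is k × m ± 42.
- 1 month: 30.4 ± 42 = day −11.6 to day 72.4.
- 3 months: 91.3 ± 42 = day 49.3 to day 133.3.
- 6 months: 182.6 ± 42 = day 140.6 to day 224.6.

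**Overlap of the first pair.** (m + 42) − (3m − 42) = 84 − 2m.
- m = 28: 28 days
- m = 30: 24 days
- m = 30.4375: 23.1 days, which is 23.1/84 = 27.5% of a window
- m = 31: 22 days

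The time origin cancels, so counting from the start or the end of radiation makes no difference.

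**Other pairs.** From 3 to 6 months the gap is 3m − 84 = 7.3 days (0 with 28-day months, where the windows just touch at day 126). For visits 6 months apart the gap is 6m − 84 = 98.6 days. The overlap is confined to the first pair.

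**When is a label really open?**
- Both early assessments exist: the earlier is the 1-month test and the later the 3-month test. Nothing is open.
- One early assessment, outside days 49 to 72: it lies in at most one window. Nothing is open.
- One early assessment, within days 49 to 72: it is open only if nobody recorded which follow-up it belonged to.

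The documents give no visit-timing data and no rate of missed visits, so the number of patients in the last group cannot be calculated from them.

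**Which analyses use the label?** The per-patient plots and the regression can use actual dates. The Kaplan-Meier endpoints need scan and event dates, not visit labels. Feasibility is timed per treatment fraction (Section 11.4). Only the t-tests at each time point use the label, and Section 13.3 permits them without requiring them.

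**Would an explicit nearest-target rule improve matters?** The midpoint between the two targets is 2m = day 60.9. Take a late 1-month test on day 65 and a 3-month test on day 95. Both lie inside their present windows, and order labels them correctly. Under nearest target, day 65 is 65 − 30.4 = 34.6 days from the first target and 91.3 − 65 = 26.3 from the second, so it moves to 3 months. Day 95 is closer (95 − 91.3 = 3.7 days) and is kept, so the 1-month value is lost. A simple rule of this kind can discard a valid observation that the plan as written would keep.

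**The case for a change.** The best case for a change is that it costs one sentence. An optional analysis still needs a defined input if it is run, and the trial is small enough for one score to matter. Patients who leave early are those for whom visit order cannot settle the label. No definition of a month removes the overlap.

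The overlap stands, and so does the absence of an allocation rule in the readable text. The Appendix C timeline is not legible beyond its note, so a rule there cannot be excluded.

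The rest carries little weight. The plan attaches the tests to follow-up visits and nowhere says that scores will be sorted afterwards by calendar day. The window reads as permission to hold a visit early or late, and overlapping permissions do not make a label ambiguous. The early opening of the 1-month window is a formality: baseline testing is listed separately in Section 4.0, and Section 11.3.5 distinguishes toxicity checks during treatment from those at follow-up. Nothing suggests that a test before or during radiation would be reported as 1-month follow-up. The wide tolerance is also a fair trade-off in patients with brain metastases, for whom strict early windows would turn late visits into missing ones.

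**Conclusion.** No change to the plan is needed. The nominal 1- and 3-month windows overlap by about 23 days (22 to 28 days for months of 31 to 28 days), and no later pair overlaps. This is an unwritten convention rather than an arithmetic error, because no stated figure is wrong. It affects at most a patient with one early assessment at about weeks 7 to 10 and no record of the intended visit. It matters only for optional t-tests on secondary endpoints in an 18-patient pilot. Following the plan as written would not lead to a wrong conclusion.

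This rests on three ordinary working assumptions: the scheduled visit and the actual date are both recorded, visit order settles the label when both early visits took place, and the trend and Kaplan-Meier analyses use actual dates. For a lone early assessment with no recorded visit, the nearest target is a sensible choice for the analyst.

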11.2 Quality of Life Evaluation

11.2.1 Functional Assessment of Cancer Therapy-Brain (FACT-Br)

This assessment is a commonly used instrument measuring general quality of life (QOL) reflecting symptoms or problems associated with brain malignancies across 5 scales: physical well-being (7 items); social/family well-being (7 items); emotional well-being (6 items); functional well-being (7 items); and concerns relevant to patients with brain tumors (23 items). Patients rate all items using a five-point rating scale ranging from "not at all" to "very much." The measure yields information about total QOL, as well as information about the dimensions of physical well-being, social/family well-being, emotional well-being, functional well-being, and disease-specific concerns. Six additional experimental items request information regarding how much each dimension affects QOL, using a "0" (not at all) to "10" (very much so) rating scale.

11.2.2 Frequency of QOL assessment

The FACT-Br will be given at baseline and at every follow-up for the first 6 months, then every 6 months thereafter (at 1, 3, 6, 12, 18, and 24 months). A window period of +/- 6 weeks will be allowed to correlate with each study time-point visit.

11.3 Toxicity and Outcome Assessments

11.3.1 Imaging followup

Patients will undergo brain MRI prior to study entry and at 1 month, 3 months and every 3 months thereafter or when otherwise indicated (eg. at onset of clinical deterioration). A window period of +/- 6 weeks will be allowed to correlate with each study time-point MRI.

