1.0 INTRODUCTION/BACKGROUND

Brain metastases are the most common adult intracranial tumor, occurring in approximately 10% to 30% of adult cancer patients, and represent an important cause of morbidity and mortality in this population.¹ The risk of developing brain metastases differs with different primary tumor histologies, with lung cancer accounting for approximately one half of all brain metastases.² The prognosis of patients with brain metastases is poor. The median survival time of untreated patients is approximately 1 month.³ With treatment, the overall median survival time after diagnosis is approximately 4 months.⁴ The RTOG recursive partitioning analysis (RPA) describes three prognostic classes, defined by age, Karnofsky Performance Score (KPS), and disease status.⁵ The most widely used treatment for patients with multiple brain metastases is WBRT. The appropriate use of WBRT can provide rapid attenuation of many neurological symptoms, improve quality of life, extend median survival, and be especially beneficial in patients whose brain metastases are surgically inaccessible or when other medical considerations preclude surgery.^{6,7} The use of adjuvant WBRT after resection or stereotactic radiosurgery (SRS) has been proven to be effective in terms of improving local control of brain metastases, and thus, the likelihood of neurological death is decreased.⁸

The majority of patients who achieve local tumor control die from progression of extracranial disease, whereas the cause of death is most often due to CNS disease in patients with recurrent brain metastases.^{7,8} Currently, no consensus on the optimal radiation schedule for patients with brain metastases is established. Standard treatment regimens include dose fractionation schemes evaluated in the early RTOG studies and range from 20 Gy in 5 fractions to 40 Gy in 20 fractions. The exact regimen used is generally at the discretion of the treating physician and often depends upon issues such as the severity of CNS symptoms, the extent of systemic disease, and physician preference.

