11.3.4 Definition of CNS progression

CNS progression will be defined as a > 25% increase in volume for any tracked brain metastasis, or the appearance of any new brain metastasis on a follow-up MRI. For lesions smaller than 1 cm in maximum diameter, a maximum increase of 50% in volume will be necessary to score as progression. This caveat is included to account for potential variability in measurement, which will be most susceptible to proportionate errors at smaller sizes. For greater than 1 cm lesions, the definition will use a 25% rule for change.

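### The ±6-week MRI window is wider than the 1-month visit itself, so a scan before or during treatment can count as the 1-month MRI and brain control read at a fixed time depends on scan timing

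*Combined protocol and SAP*

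**What the plan says.** Section 11.3.1 sets the imaging schedule: "Patients will undergo brain MRI prior to study entry and at 1 month, 3 months and every 3 months thereafter or when otherwise indicated". It then allows ±6 weeks around each of these scans: "A window period of +/- 6 weeks will be allowed to correlate with each study time-point MRI". The note to Appendix C repeats the allowance, with no exception for the first visit: "A window period of +/- 6 weeks will be allowed to correlate with each study time-point and MRI visit".

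Section 11.3.4 defines CNS progression as volume growth of a tracked lesion beyond a threshold, "or the appearance of any new brain metastasis on a follow-up MRI". Local and regional brain control are primary endpoints (13.1.1), and locoregional control is a primary objective (2.1.2). Section 13.3 gives the method: "Local control, regional brain control, progression-free survival and overall survival will be assessed using the Kaplan-Meier method with censoring as appropriate". The curves are then to be compared with published results.

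The readable text gives no origin for the 1-month visit, no rule for dating a failure, no method for interval-censored data and no time at which control will be read. The Appendix C table did not survive in the text available, so the origin may be stated there.

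**The concern.** A window should keep a scan close enough to its visit to stand for that visit. Six weeks is longer than one month, so at the first visit it does not.

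A new or growing lesion arises at some point between the last clear scan and the first positive one. With no other dating rule, Kaplan-Meier would place the failure at the scan that detects it. The estimate at a fixed time then reflects the scan calendar as well as the disease. A confidence interval does not show that part, and it carries into the comparison with published series, which may have been imaged on other schedules. The same applies to the CNS component of progression-free survival.

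**Working it through.** The plan states no expected control rate and does not derive the 18 patients, so there is no figure of its own to reproduce. Two checks apply.

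**1. Window arithmetic.** Inputs: visits at 1, 3, 6, 9 and 12 months and a window of ±42 days (11.3.1); 10 fractions (6.3.2). Assumptions: 1 month = 30.44 days; weekday fractions starting on a Monday, so the first is day 0 and the last is day 11.

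| Visit | Nominal day | Window (days) |
|---|---|---|
| 1 month | 30.4 | -12 to 72 |
| 3 months | 91.3 | 49 to 133 |
| 6 months | 182.6 | 141 to 225 |
| 9 months | 273.9 | 232 to 316 |
| 12 months | 365.2 | 323 to 407 |

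- Earliest 1-month scan, counted from treatment start: 30.4 - 42 = day -11.6.
- The same, counted from the last fraction: 11 + 30.4 - 42 = -0.6, about the first fraction.
- Overlap of the 1- and 3-month windows: 72.4 - 49.3 = 23 days. One scan in that span could serve both visits.
- If the 1-month scan was taken before treatment, the first scheduled post-treatment scan can be at 91.3 + 42 = day 133. That is later than the 4-month toxicity point in 13.2 (4 × 30.44 = day 122).
- Gap between adjacent 3-monthly scans: 91.3 - 84 = 7 days to 91.3 + 84 = 175 days.

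**2. Effect on the control estimate.** If failures are dated at the detecting scan and nobody is censored, Kaplan-Meier at time t returns the true control at the last scan on or before t. Assume exponential failure, S(t) = 0.5^(t/median), with median 6 or 12 months, and no unscheduled scans. Reading at 6 months:

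| Scan pattern | Last scan on or before 6 months | Median 6 | Median 12 |
|---|---|---|---|
| On time | 6.00 months | 50% | 71% |
| All 6 weeks early | 4.62 months | 0.5^(4.62/6) = 59% | 0.5^(4.62/12) = 77% |
| All 6 weeks late | 4.38 months | 0.5^(4.38/6) = 60% | 0.5^(4.38/12) = 78% |
| Spread evenly over windows (simulated) | varies | 63% | 79% |

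From the unrounded values, the shift from on-time scanning is 9 to 13 points with median 6 (50.0% to between 58.6% and 62.6%) and 6 to 8 points with median 12 (70.7% to between 76.6% and 78.9%).

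**Direction.** Read just before 6 months, the on-time schedule has its last scan at 3 months and shows 0.5^(3/6) = 71% (median 6). The late schedule still shows 60%. The order has reversed.

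**Scale.** The 95% half-width at 6 months with 18 patients is 1.96 × √(0.5 × 0.5/18) = 23 points, or 1.96 × √(0.707 × 0.293/18) = 21 points.

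**The case against.** The best case for leaving the plan alone has four parts.

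- **Unscheduled scans are allowed.** Section 11.3.1 provides for MRI when otherwise indicated, including when a patient worsens. This stands: symptomatic failures would be found sooner, and the shifts above are too large to that extent. Silent new lesions still wait for the next scan.
- **Kaplan-Meier dated at detection is conventional.** The published comparators may well use it, and an interval-censored curve from 18 patients is coarse. This stands against replacing Kaplan-Meier, but not against a supporting analysis.
- **The study is a small descriptive pilot.** Sampling error exceeds the shift, and 13.3 attaches no threshold to the control rate. This limits the importance of the point. The shift is nevertheless not random error, and more patients would not remove it.
- **Local control may hardly move.** Section 1.0 reports no local failure in 12 earlier patients. If 6-month local control were 95% (an assumption), a last scan at day 133 would give 0.95^(133.3/182.6) = 96%. The point is therefore mainly about regional control.

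A reader might go further and infer that late scanning always flatters the treatment. The reversal just before 6 months shows that it does not. A reader might also construct much larger distortions. With an assumed true 6-month control of 65%, a last scan at day 49 gives 0.65^(49.3/182.6) = 89%. That needs the whole cohort scanned 6 weeks early at 3 months and 6 weeks late at 6 months. The windows permit this, but nothing in the documents suggests it.

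Nor do the documents support a claim that about half the patients would die unscanned. That figure comes from applying the background statement "With treatment, the overall median survival time after diagnosis is approximately 4 months" to a first scan at 4.4 months: 1 - 0.5^(4.38/4) = 53%. It ignores unscheduled MRI. It also uses a median for treated patients overall, whereas this trial enrols only KPS of at least 70 and RPA class I or II (3.1).

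**Conclusion.** The window rule is defective as written. That part needs no assumed control rate: on either time origin, the 1-month window opens before treatment has finished, and it overlaps the 3-month window.

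The effect on the endpoint is real but moderate: about 6 to 13 points at 6 months. This rests on exponential failure with median 6 or 12 months, no censoring, no unscheduled scans, failure dated at the detecting scan (inferred, since no other rule is given) and a 6-month reading time that the plan does not itself set. The direction changes with the reading time. Whether the earliest scan falls before treatment or only during it depends on the time origin, which the readable text does not give.

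**What to change.** 1. In 11.3.1 and Appendix C, state the time origin, require the 1-month MRI to fall after the last fraction, and narrow the windows so that they do not overlap and one scan cannot serve two visits. For example, ±2 weeks at 1 month gives day 16 to 44, and ±4 weeks at 3 months gives day 63 to 119. With ±4 weeks at later visits, adjacent 3-monthly scans are at most 91.3 + 56 = 147 days apart; with ±3 weeks, 91.3 + 42 = 133 days.
2. In 13.3, keep Kaplan-Meier for comparability with published curves and state how failures are dated. Add, as a supporting analysis, an interval-censored estimate of local and regional control from actual scan dates, running from the last clear scan to the first positive one.

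Both parts are needed. Narrower windows do not stop a scan just after the reading time from pushing its failures past it, and no analysis recovers post-treatment status from a pre-treatment scan. The cost is some more logged visit deviations and a little more analysis; no scans are added.
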